9.1 Adverse Event Assessment

9.1.1 Adverse Events

AE definitions are provided in Table 5. AEs that are potentially system related or procedure related as well as stroke, TIA, bleeding events, and ablation-related events will be collected and reported to Medtronic during the study, starting from the time the subject completes consent. Reporting of these events to Medtronic will occur on the AE eCRF.

Each AE must be recorded on a separate AE eCRF and include a description of the event, the diagnosis, the date of event onset, the date the site became aware of the event, the relatedness and seriousness of the event, diagnostic tests and procedures performed, actions taken as a result of the event, and the outcome of the event. Documented pre-existing conditions are not considered AEs unless the nature or severity of the condition has worsened. Additionally, detected arrhythmias (including AF) for which no intervention is made are not reportable as AEs. In all geographies, Unavoidable AEs, listed in Table 5 need not to be reported if resolved within the timeframe specified.

For AEs that require immediate reporting (see Table 7), initial reporting may be done by phone, or on the CRF completing as much information as possible. The AE CRF must be completed as soon as possible.

In case the investigator requires information from the sponsor in an emergency situation, the investigator can contact the study sponsor (Table 1).

An assessment for Device Related, Procedure-Related Events as well as stroke, TIA, bleeding events, and ablation-related events will be conducted at each subject follow-up. Submit any

additional supporting evidence which could assist in the assessment and review of reported events e.g. device transmissions and/or device uploads.

9.1.2 *Device Deficiencies*

Device deficiency information will be collected throughout the study and reported to Medtronic. Device deficiencies that did not lead to an Adverse Event should be reported as a device deficiency only.

9.1.3 *Processing Updates and Resolution*

For any changes in status of a previously reported AE (i.e. change in actions taken, change in outcome, change in relatedness), an update to the original AE must be completed. All reported AEs must be followed until the AE has been resolved, is unresolved with no further actions planned, the subject exits the study or until study closure, whichever occurs first.

In the event that a subject is exited from the study prior to study closure, all efforts should be made to continue following the subject until all unresolved procedure or system related AEs, as classified by the investigator, are resolved or they are unresolved with no further actions planned.

At the time of study exit, all AEs with an outcome of “Unresolved, further actions or treatment planned” must be reviewed and an update to the original AE must be reported. At a minimum, if there are no changes to the description, relatedness, test and procedures or actions taken, the outcome must be updated to reflect “Unresolved at time of study closure.”

9.2 Adverse Event and Device Deficiency Definitions

All reportable AEs and device deficiencies will be reviewed by a Medtronic representative. AEs will be classified according to the definitions provided.

Where the definition indicates “device”, it refers to any device used in the study. Refer to Appendix I for event definitions. Every effort has been made to align study definitions with the ISO 14155:2011 standard but since the study is not within the scope of ISO, minor modifications have been made to better align with the purpose of the study. Specifically, the reference to the term “investigational” has been removed from the definitions with all other content unchanged.

Table 5: Adverse Event Definitions

General	
Adverse Event (AE) (ISO 14155-2011, 3.2)	
Any untoward medical occurrence, unintended disease or injury, or untoward clinical signs (including abnormal laboratory findings) in subjects, users or other person, whether or not related to the medical device
 
Note 1: This definition includes events related to the medical device or the comparator
 
Note 2: This definition includes events related to the procedure involved
 
Note 3: For users or other persons, this definition is restricted to the medical device.

Adverse Device Effect (ADE) (ISO 14155:2011, 3.1)	
Adverse event related to the use of a medical device.
 
Note 1: This definition includes any adverse event resulting from insufficient or inadequate instructions for use or the deployment, implantation, installation, or operation, or any malfunction of the medical device.
 
Note 2: This definition includes any event resulting from user error or from intentional misuse of the medical device

Device Deficiency (DD) (ISO 14155:2011, 3.15)	
Inadequacy of a medical device with respect to its identity, quality, durability, reliability, safety or performance.
 
NOTE: Device deficiencies include malfunctions, use errors and inadequate labeling

Relatedness	
Procedure Related	An adverse event that occurs that is directly related to the implantation or modification of the Reveal LINQ system.
System Related	An adverse event that results from the presence or performance (intended or otherwise) of any component of the system (including: Reveal LINQ ICM, Programmer, Patient Assistant, and MyCareLink Patient Monitor).
Seriousness	
Serious Adverse Event (SAE) (ISO 1455-2011, 3.37)	
An Adverse Event that:
 
 a) led to a death, b) led to a serious deterioration in the health of the subject, that either resulted in 
 1. a life-threatening illness or injury 2. a permanent impairment of a body structure or a body function 3. in-patient hospitalization or prolongation of existing hospitalization 4. medical or surgical intervention to prevent permanent impairment to body structure or a body function c) led to foetal distress, foetal death or a congenital abnormality or birth defect. 
Note: Planned hospitalization for a pre-existing condition without serious deterioration in health is not considered a serious event

Serious Adverse Device Effect (SADE) (ISO14155-2011, 3.36)	Adverse device effect that has resulted in any of the consequences characteristic of a serious adverse event
Unanticipated Serious Adverse Device Effect (USADE) (ISO14155:2011, 3.42)	
Serious adverse device effect which by its nature, incidence, severity or outcome has not been identified in the current version of the risk analysis report.
 
Note: Anticipated serious adverse device effect (ASADE) is an effect which by its nature, incidence, severity or outcome has been identified in the risk analysis report.

Other																	
Unavoidable Adverse Event	An Adverse Event inherent to a surgical procedure that is expected to occur in all subjects for a projected duration according to the Investigator's opinion, including, but not limited to: 
  
 Event Description	Time (hrs) from end of Procedure	
   
 Anesthesia related nausea / vomiting	24 hrs	
 
 Low-grade fever (<100°F or < 37.8°C)	48 hrs	
 
 Pocket site / incisional pain	72 hrs	
 
 Mild to moderate bruising / ecchymosis	168 hrs (7 days)	
 
 Sleep problems (insomnia)	72 hrs	
 
 Back pain related to laying on the table	72 hrs	
 
 Shoulder pain / discomfort / stiffness / related to shoulder immobilization during procedure	72 hrs	
  
	Event Description	Time (hrs) from end of Procedure	Anesthesia related nausea / vomiting	24 hrs	Low-grade fever (<100°F or < 37.8°C)	48 hrs	Pocket site / incisional pain	72 hrs	Mild to moderate bruising / ecchymosis	168 hrs (7 days)	Sleep problems (insomnia)	72 hrs	Back pain related to laying on the table	72 hrs	Shoulder pain / discomfort / stiffness / related to shoulder immobilization during procedure	72 hrs
Event Description	Time (hrs) from end of Procedure																
Anesthesia related nausea / vomiting	24 hrs																
Low-grade fever (<100°F or < 37.8°C)	48 hrs																
Pocket site / incisional pain	72 hrs																
Mild to moderate bruising / ecchymosis	168 hrs (7 days)																
Sleep problems (insomnia)	72 hrs																
Back pain related to laying on the table	72 hrs																
Shoulder pain / discomfort / stiffness / related to shoulder immobilization during procedure	72 hrs																
Infection	
Infection will be defined as deep incision site or superficial infection.
 
Deep incision site are classified as pain, redness, or drainage at incision site requiring the device to be removed or IV antibiotics administered.
 
Superficial infections are defined as redness beyond procedure expectation and oral antibiotics administered.
 
For both deep incision and superficial infections, a physician directed intervention must occur for the event to be defined as an infection.
																

9.3 Adverse Events and Deficiency Classification

All reportable AEs and device deficiencies will be reviewed by a Medtronic representative. AEs will be classified according to the definitions provided.

The site will report the clinician's assessment of the event relative to relatedness (e.g. device or procedure) and seriousness. Upon receipt of AEs at Medtronic, a Medtronic representative will review the AE /device deficiency for completeness and accuracy and when necessary will request clarification and/or additional information from the Investigator. Medtronic will utilize MedDRA, the Medical Dictionary for Regulatory Activities, to assign a MedDRA term for each AE based on the information provided by the investigator.

Regulatory reporting of all safety events, which may include SAEs and device deficiencies that could have led to an SADE, will be completed according to local regulatory requirements.

AEs and Deaths will be classified according to the standard definitions as outlined below:

Table 6: Adverse Event classification responsibilities

What is classified?	Who classifies?	Classification Parameters
Relatedness	Investigator	System-related (including: Reveal LINQ ICM, Programmer, Patient Assistant, and MyCareLink Patient Monitor), Procedure-related
	Sponsor	System-related (including: Reveal LINQ ICM, Programmer, Patient Assistant, and MyCareLink Patient Monitor), Procedure-related
Severity	Investigator	SAE, SADE
	Sponsor	SAE, SADE, USADE, Complication or Observation (for all system or procedure related AEs), Life Threatening
Diagnosis	Investigator	Based on presenting signs and symptoms and other supporting data
	Sponsor	MedDRA term assigned based on the data provided by Investigator
Death Classification	Investigator	Sudden Cardiac, Non-sudden Cardiac, Non-Cardiac, Unknown

9.4 Adverse Event and Device Deficiency Reporting Requirements

Regulatory reporting of AEs/DDs will be completed according to local regulatory requirements. Refer to Table 7: Adverse Event Reporting Requirements for a list of required investigator reporting requirements and timeframes, and of required Medtronic reporting requirements and timeframes. Each geography has the responsibility to follow current local reporting requirements.

The investigator is required to report SAEs and SADEs/USADEs to Medtronic immediately, and to the Ethics Committee per local requirements. Medtronic is also required to report these events to the local regulatory authority based on their requirements. It is the responsibility of the investigator to abide by any additional AE/DD reporting requirements stipulated by the Ethics Committee responsible for oversight of the study.

For AEs/DDs that require immediate reporting, initial reporting may be done by contacting the study sponsor per the sponsor contact information provided in this document.

The reporting of product complaints is not part of the clinical study and should be done in addition to the Adverse Event reporting requirements. It is the responsibility of the investigator to report all product complaint(s) associated with a medical device distributed by Medtronic, regardless whether they are related to intended use, misuse or abuse of the product. Reporting must be done immediately and via the regular channels for market released products.

Table 7: Adverse Event Reporting Requirements

Serious Adverse Events (SAEs)	
Investigator submit to:	
Medtronic	
EMEA: Immediately after the investigator first learns of the event or of new information in relation with an already reported event. (ISO 14155 and local law)
 
All other geographies: Report to the sponsor, without unjustified delay, all serious adverse events.

Ethics Committee	All geographies: Submit per local Ethics Committee requirement.
Regulatory authorities	All geographies: As per local reporting requirement.
Sponsor submit to:	
Regulatory authorities	All geographies: Submit to regulatory authority per local reporting requirement.
Ethics Committee	All geographies: Submit to Ethics Committee per local reporting requirement.
Serious Adverse Device Effects (SADEs) including Unanticipated Serious Adverse Device Effects(USADEs)	
Investigator submit to:	
Medtronic	
EMEA: Immediately after the investigator first learns of the event or of new information in relation with an already reported event. (ISO 14155 and local law)
 
All other geographies: Submit in a timely manner after the investigator first learns of the event.

Regulatory authorities	All geographies: As per local reporting requirement.
Ethics Committee	All geographies: Submit per local Ethics Committee requirement.
Sponsor submit to:	
Regulatory authorities	All geographies: Submit to regulatory authority per local reporting requirement.
Ethics Committee	All geographies: Submit to Ethics Committee per local reporting requirement.
Adverse Device Effects	
Investigator submit to:	
Medtronic	
EMEA: Immediately after the investigator first learns of the effect. (ISO 14155 and local law)
 
All other geographies: Submit in a timely manner after the investigator first learns of the effect.

Regulatory authorities	All geographies: As per local reporting requirement.
Ethics Committee	All geographies: Reporting timeframe as per local Ethics Committee requirement.
Sponsor submit to:	
Regulatory authorities	All geographies: Submit to regulatory authority per local reporting requirement.

Ethics Committee	All geographies: Submit to Ethics Committee per local reporting requirement.
All other reportable Adverse Events	
Investigator submit to:	
Medtronic	All geographies: Submit in a timely manner after the investigator first learns of the event.
Regulatory Authorities	All geographies: Submit to regulatory authority per local reporting requirement.
Ethics Committee	All geographies: Submit to Ethics Committee per local reporting requirement.
Sponsor submit to:	
Regulatory authorities	All other geographies: Submit to regulatory authority per local reporting requirement.
Device Deficiencies	
Investigator submit to:	
Medtronic	All geographies: Submit in a timely manner after the investigator first learns of the event.
Regulatory Authorities	All geographies: Submit to regulatory authority per local reporting requirement.
Ethics Committee	All geographies: Submit to Ethics Committee per local reporting requirement.

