9. ADVERSE EVENTS AND DEVICE DEFICIENCIES

Reporting and analysis of safety data are mandated by regulatory authorities worldwide. Medtronic has established procedures in conformity with worldwide regulatory requirements to ensure appropriate reporting of safety information. This study is conducted in accordance with these procedures and regulations.

Since the safety reporting requirements and classification systems vary for each regulatory agency, requirements from all geographies are taken into account for the collection and reporting of safety information.

The Reveal LINQ ICM is approved with demonstrated evidence of safety and effectiveness for their intended use. It is not the purpose of the study to demonstrate product safety and effectiveness for the purpose of obtaining product approval nor to obtain approvals for expanded indications of use, new material or design change for medical device already on the market.

For the Reveal LINQ registry, all AEs occurring after consent that are potentially system related or procedure related will be collected, as well as:

- Stroke
- Transient ischemic attack (TIA)
- Bleeding events, and
- Ablation-related events
 - Espophageal injury, phrenic nerve injury, PV stenosis/occlusion, silent microembolism, late hematoma, pseudoaneurysm, AV fistula, dry cough, hemoptysis, other

In all geographies, Unavoidable AEs, listed in Table 5 need not to be reported if resolved within the timeframe specified.

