6.10. Safety Evaluation

Adverse events will be summarized by relatedness (procedure & component (ICM, insertion tool, incision tool, other)), seriousness, and event primary diagnosis.

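### Protocol Sections 9 and 9.1.1 limit which adverse events are collected, while Section 9.4 and Table 7 ask for SAEs without that limit, so the overall and unrelated counts in SAP 6.10 have no single definition

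*Protocol*

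**What the plan says.** **Narrow scope.** Protocol Section 9 states that "all AEs occurring after consent that are potentially system related or procedure related will be collected, as well as" four named types: stroke, TIA, bleeding events and ablation-related events. Section 9.1.1 repeats this: "AEs that are potentially system related or procedure related as well as stroke, TIA, bleeding events, and ablation-related events will be collected and reported". Seriousness plays no part in either sentence. Section 9.1.1 also fixes what sites are prompted for: "An assessment for Device Related, Procedure-Related Events as well as stroke, TIA, bleeding events, and ablation-related events will be conducted at each subject follow-up".

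**Broad scope.** The text of Section 9.4 obliges the investigator to report SAEs, SADEs and USADEs to the sponsor at once, without reference to relatedness or event type. The SAE row of Table 7 says, for geographies other than EMEA: "Report to the sponsor, without unjustified delay, all serious adverse events". Table 5 (Section 9.2) defines an SAE as an AE meeting a seriousness criterion, and an AE is counted "whether or not related to the medical device".

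**Arrhythmias.** Section 9.1.1 adds that "detected arrhythmias (including AF) for which no intervention is made are not reportable as AEs". It does not say how a detected arrhythmia that does lead to an intervention is to be handled.

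**Analysis.** SAP 6.10: "Adverse events will be summarized by relatedness (procedure & component (ICM, insertion tool, incision tool, other)), seriousness, and event primary diagnosis". It does not limit the summaries to the Section 9 event classes. SAP 6.3 pools all centers.

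**The concern.** The point is which events are collected, not how quickly they are reported. Two sites can follow the protocol in good faith and send different sets of SAEs. A site working from Sections 9 and 9.1.1 would leave out an unplanned admission for pneumonia with serious deterioration. A site working from Section 9.4 and Table 7 would report it.

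Pooled, the total SAE count would then be neither an all-cause count nor a count of the Section 9 classes. Unrelated SAEs would also arrive unprompted, because the follow-up assessment does not ask for them, so even a site following the broad rule may capture them incompletely. The registry is meant to produce reliable long-term data that may go to a regulator (Section 2.1), and a safety table should have one definition of what was collected.

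**Working it through.** No rate, power or sample-size figure is in question and the plan states no expected SAE count, so the check compares the passages.

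**Step 1. Classify each type of event under both rules.**

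| Event | Sections 9 and 9.1.1 | Section 9.4 and Table 7 |
|---|---|---|
| System- or procedure-related SAE | collected | reported |
| Serious stroke, TIA, bleeding or ablation-related event | collected | reported |
| Non-fatal unrelated SAE of any other type | not collected | reported |
| Death | reported under Section 7.12 | reported under Section 7.12 |

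The rules part only in the third row. Table 5 narrows that row a little: hospitalization counts only with a serious deterioration in health, and planned admission for a pre-existing condition without such deterioration is excluded.

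**Step 2. Look for a sentence that settles it.** Sections 9.2 and 9.3 speak of reportable AEs, and the residual row of Table 7 covers other reportable AEs. Neither says that the SAE row is confined to the Section 9 list, and no section says which rule prevails.

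**Step 3. Follow the events into the SAP.** Let R be the SAEs in the first two rows of the table and U those in the third. A site following the narrow rule contributes R. A site following the broad rule contributes R + u, where u is the part of U it happens to report (0 ≤ u ≤ U). Summed over sites,

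pooled count = ΣR + Σu, with the second sum over broad-rule sites only.

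This lies between ΣR and Σ(R + U). Where it falls depends on how sites read the protocol. The documents give neither U nor the share of sites using each rule, so only the direction is known: the broad rule yields at least as many SAEs as the narrow one.

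**Step 4. Separate what is affected from what is not.**

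- Affected in SAP 6.10: the total, the unrelated category, and the breakdowns by seriousness and by primary diagnosis.
- Not affected: system- and procedure-related SAE counts, which are in scope under both rules, and the count of deaths.
- Primary Objective 1 is not affected. SAP 6.9 takes it from the Follow-up CRF and the Treatment log, not from the Event CRF.
- Primary Objective 2 should be largely unaffected, since procedure-related incision-site infections are in scope either way. The SAP numerator has no relatedness filter, so an unrelated serious infection could enter only if a site marked it as an infection contrary to the incision-site definition in Table 5.

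**Step 5. Arrhythmias.** The exemption covers detected arrhythmias without intervention. Treated arrhythmia is not on the Section 9 list, so whether one is reportable when it is not system or procedure related is left to inference.

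**The case against.** The best defence is that the two rules do different jobs: Section 9 sets what is collected and Table 7 sets when it is reported. Section 9.1.1 sends sites to Table 7 for events needing immediate reporting, the residual row of Table 7 refers to reportable events, and the follow-up assessment prompts only for the narrow list. This reading is plausible and may be what the sponsor intended. It is not stated, though. Section 9.4 presents Table 7 as giving requirements as well as timeframes, the SAE row says *all*, and device effects have a separate row, so the SAE row naturally reaches further than device-related events.

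A second defence is that SAP 6.10 already splits by relatedness, so related events can be separated out. That stands, and it is why the related counts are safe. It does not give a meaning to the total or to the unrelated category.

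A reader might go further in three ways that the documents do not support:

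- **A regional difference in scope.** The word *all* appears only in the non-EMEA entry. The EMEA entry sits under the same SAE heading and gives timing, and the text of Section 9.4 covers every geography.
- **Double counting of the Primary Objective 1 outcome.** That outcome does not come from the Event CRF. Nor does exempting untreated arrhythmias by itself make every treated one reportable.
- **A numerical bias.** The 0.7% and 1.6% in Section 3 are procedure-related SAEs from earlier studies. Section 9 also covers system-related events and the four named types, so those figures are not the SAE share under the narrow rule. Any unrelated-SAE rate or split of sites would be a guess, and SAP 6.10 names no percentages.

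**Conclusion.** The inconsistency is real and nothing in the documents resolves it. It concerns non-fatal, unrelated SAEs outside the four named types, together with unclear wording on arrhythmias that lead to an intervention. As a result, the total, unrelated, by-seriousness and by-diagnosis adverse event counts in SAP 6.10 would depend on which rule each site followed. The size cannot be calculated from the documents; the direction is that broad-rule sites report the same number of SAEs or more.

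The conclusion assumes that some sites read Section 9.4 and Table 7 literally and others apply the Section 9 limit. If all sites worked to one scope and captured it fully, the mixture would not arise. This is a clarification of the safety tables and site instructions. It is not a threat to the related-event counts, to deaths or to Primary Objective 1.

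**What to change.** 1. **Protocol.** Reconcile Sections 9, 9.1.1 and 9.4 and Table 7 so that they state one SAE collection scope. The wording in 9.1.1 on detected arrhythmias, with and without intervention, should be brought into line at the same time. The choice of scope is the sponsor's, and local law must be respected. If all SAEs are chosen, the assessment at each follow-up should prompt for them.
2. **SAP 6.10.** Base the summary tables on the Section 9 classes: system related, procedure related, stroke, TIA, bleeding and ablation related. Put any other reported SAE in a separate listing without a rate, unless the reconciled protocol collects all SAEs at every site. The listing also takes any extra SAEs that local law obliges some sites to report.

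The cost is a wording change in the protocol sections and a sentence in SAP 6.10. The SAP change can be made without amending the protocol, and it removes the mixture from the summary tables. The small downside is that unrelated SAEs already collected would appear only in a listing.
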